Obstructive sleep apnoea (OSA) in adults has been correlated with the degree of blood pressure elevation above normal and thereby with the increasing risk of hypertension (HT).⁽¹³⁾ Thus, it is internationally accepted that OSA should be considered as a cause of both primary HT and secondary HT.^(1, 6, 7) The evidence has shown that OSA is linked with uncontrolled high blood pressure, more precisely, OSA has a close and strong relationship with RHT⁽¹⁾ and is cited as the most common secondary cause.⁽¹⁴⁾ Further, limited studies indicate, OSA has been associated with cardiac structure and function.⁽¹⁵⁾ However, relatively few studies have identified an association between OSA and TRHT.

It follows that since the severity of OSA is associated with major modifiable risk factors such as obesity and hyperaldosteronism in patients with RHT,⁽¹⁶⁾ reducing OSA through modifying the risk factor/s may be highly beneficial. Treatment for OSA is wide ranging and may include continuous positive airway pressure (CPAP).⁽¹⁷⁾ However, the goal of CPAP intervention is more to reduce symptoms rather than addressing the cause.⁽¹⁸⁾ Furthermore patient compliance is often low, due to the frustrations associated with the CPAP mask.⁽¹⁹⁾ Rather than just focusing on symptomatic management of OSA, it is suggested that new therapeutic strategies, that address OSA and HT simultaneously, may be more effective.⁽¹⁶⁾ In addition to CPAP management for OSA described above, increasing physical activity may be beneficial in treating both OSA⁽²⁰⁾ and BP⁽²¹⁾ as compliance with a prescribed physical activity programme can lead to a reduction in BP, and thereby, a reduction in the number of antihypertensive medications required by patients with HT.^(6, 7, 9, 22)

3. Aim of Study

To investigate the association between true resistant hypertension and high risk of obstructive sleep apnoea in a sub group of individuals diagnosed with resistant hypertension.

4. Objectives

To:

- determine the prevalence of true resistant hypertension (TRHT) measured by 24h ambulatory blood pressure monitoring in Dunedin based individuals with resistant hypertension (RHT);
- investigate the relationship between Epworth Sleepiness Scale scores and sleep fragmentation in the Dunedin based individuals identified with true resistant hypertension (TRHT);
- investigate the association between true resistant hypertension (TRHT) and high risk of obstructive sleep apnoea (OSA), in the Dunedin based individuals

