The population will comprise adults with resistant hypertension (RHT), based in the Dunedin region, aged 60 years and younger, who have been diagnosed with high blood pressure and are on three or more pharmacological agents of different classes including a diuretic. The population has been drawn from the Ministry of Health Pharmaceutical Collection Warehouse, via the Best Practice Advocacy Centre (bpac),⁽²³⁾ New Zealand.

The total number of adults with hypertension and being pharmacologically managed with three or more antihypertensive medications (estimated RHT) in New Zealand is 100,340; Southern District Health Board, 8425; and in the Dunedin region, 3184. The number of adults 60 years age or below in the Dunedin region with RHT is 559.⁽²⁴⁾

9. Eligibility Criteria

Inclusion criteria

- Age: 18-60 years inclusive
- Gender: all
- Able to communicate/follow instructions in English
- Based in Dunedin region
- Diagnosed with hypertension
- Prescribed three or more antihypertensive medications including a diuretic (RHT definition⁽⁹⁾).

Exclusion criteria

- Diagnosed with hypertension prescribed two or less antihypertensive medications
- Adults above the age of 60 years
- Diagnosed/known renal disease
- Females who are pregnant

10. Study Outcomes

Primary Outcome

The prevalence of TRHT in a population with RHT and the association of TRHT with high risk of OSA.

Secondary Outcome(s)

The correlation between increased Epworth Sleepiness Scale score and sleep fragmentation in the subset with true resistant hypertension.

11. Study Procedures

a. Recruitment of participants

Adults (18-60y) in the Dunedin region, [anonymized] on three or more pharmacological agents of different classes, and the general practices [anonymized] they are enrolled at, have been identified from the Ministry of Health Pharmaceutical Collection Warehouse, via the Best Practice Advocacy Centre (bpac),⁽²³⁾ New Zealand. The number of adults on the list is 559⁽²⁴⁾, [the list of names will remain de-identified to the research team as letters will be forwarded by General Practitioners].

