The PI will obtain the participant's demographic data (age; gender; ethnicity); general health and habits, physical activity level (initial assessment form – Appendix 1), quality of life (SF-36: Appendix 2) and OSA risk (ESS: Appendix 3), using self-administered questionnaires. Participants will use a tablet computer to complete this section which will take approximately 20 minutes. Data will then be downloaded onto the study data base (MS Excel).

The PI will then take the participant's resting blood pressure (office blood pressure – (BP)), heart rate, and peripheral saturation using standardised, calibrated equipment (NT1A Pulse oximeter, New Tech, Hamburg, Germany and Omron automatic digital blood pressure monitor, HEM 7322, Netherlands) and in accordance with the

ACC/AHA 2017 guidelines.⁽⁶⁾ Next, the PI will take the anthropometric (body weight, height and circumferences of neck, waist, hip,) measurements of the participant using standard guidelines⁽²⁵⁾ and equipment; electronic weighing scale (kg) and stadiometer (cm), measuring tape (scale in cm); with two decimal point accuracy. The equipment will be calibrated as required. This section of the procedure will take about 15 minutes. The variables, body mass index (BMI) and waist to hip ratio will be calculated using simple formulas on MS Excel.

The subset with RHT who also score ≥ 9 on the Epworth Sleepiness Scale (ESS) will be identified as 'at risk for OSA', and will be fitted with 24h ambulatory blood pressure monitor on the non-dominant upper arm, at the Cardiology Research Laboratory, on 9th floor in Dunedin Hospital. The participant will be advised to undertake daily activities/sleep as usual over the next 24 hours.

Appointment 2:

On the following day the device will be removed at the same setting, the Cardiology Research Laboratory, and data downloaded to confirm TRHT or not. Where TRHT is confirmed the participant will have an echo cardiogram to confirm baseline left ventricular function (results to be interpreted by co-investigator cardiologist).

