A statistician was consulted to confirm the calculation of the sample size based on the population with RHT in Dunedin region (559). Thus, the sample size is $n=83$, with 95% confidence level and 10% margin of error. The recruitment target is set at $n=100$ and with the dropout rate of up to 20%, the estimated sample size ($n=83$) is expected to be able to be fulfilled.

The cohort with true resistant hypertension and high risk of OSA is unknown for the Dunedin based population with RHT. An 18% response rate will be sufficient to achieve the target sample size ($n=100$) for the study.

12b. Statistical methods

Simple statistics (mean, standard deviation, range) will be used to describe the demographic data and the measurements (anthropometry /blood pressure/ /sleep/activity/cardiac parameters) of the population with RHT in Dunedin region and in the sub population with TRHT and high risk of OSA. The data for anthropometrics, blood pressure, activity and cardiac parameters will be compared with accepted international guidelines,⁽²⁵⁾ and questionnaires will be interpreted using standard descriptors.

The relationship between the anthropometry parameters, blood pressure, ESS score, cardiorespiratory fitness, and activity and sleep levels with TRHT will be determined using regression analysis.

The statistical package for social sciences (SPSS) version 25.0 or above for Windows (IBM SPSS version 25.0 or above), NY, USA⁽¹⁰⁾ will be used for the data analysis.

13. Ethical Considerations

The study to be conducted will conform fully with the principles of the “Declaration of Helsinki”, Good Clinical Practice (GCP) and within the laws and regulations of New Zealand. The study has been registered on the Australian New Zealand Clinical Trials Registry (ANZCTR). Ethical clearance will be obtained from the HDEC, New Zealand prior to commencing the study.

No identifiable information will be used in the study. For the identification of the cohort, the adults in the Dunedin region, who meet the criteria for RHT, on three or more pharmacological agents of different classes, including diuretic, have been identified (by bpac from the Ministry of Health Pharmaceutical Collection Warehouse and categorised to the various general practices. Letters supplied will be sent to those identified from their General Practitioner by linking names and addresses to national health numbers)

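### Section 12b relates the ESS score to TRHT only as present or absent; a companion regression on 24h mean pressure would recover information at almost no cost, but the ESS ≥ 9 gate to monitoring is the larger problem

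*Protocol*

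**What the plan says.** Section 10 makes the association part of the primary outcome: "The prevalence of TRHT in a population with RHT and the association of TRHT with high risk of OSA". The Introduction also calls it a key outcome measure.

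Under Section 11c, Appointment 2, the ambulatory recording is reduced to a status: "data downloaded to confirm TRHT or not". Section 12b then relates a list of measures, including the ESS score, to that status: ESS score, fitness "and activity and sleep levels with TRHT will be determined using regression analysis". No regression form is named, and no analysis of the 24h mean pressure itself against ESS is specified.

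The Background gives a graded rationale: "Obstructive sleep apnoea (OSA) in adults has been correlated with the degree of blood pressure elevation above normal".

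Under Section 11c, Appointment 1, participants who "score ≥ 9 on the Epworth Sleepiness Scale (ESS) will be identified as 'at risk for OSA" are the ones fitted with the 24h monitor. The Introduction says the same.

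Section 12a sets the sample size on precision for a proportion: "Thus, the sample size is $n=83$, with 95% confidence level and 10% margin of error". It gives no effect size or power for the association.

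**The concern.** A threshold is needed to diagnose TRHT and report its prevalence. It is not needed to ask whether OSA risk rises with pressure on treatment. Turning a measured pressure into a yes/no status treats a participant just above the threshold like one far above it, and so weakens any graded relationship.

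This matters because the association is part of the primary outcome while the sample size was set for something else. A non-significant TRHT result could be read as showing no link with OSA risk when the analysis scale had discarded part of the evidence.

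**Working it through.** **Inputs from the protocol.** Population 559 (Section 8: "The number of adults 60 years age or below in the Dunedin region with RHT is 559"); 95% confidence, ±10% margin and n = 83 (Section 12a).

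**Assumptions (not in the protocol).** ESS and 24h pressure bivariate normal with correlation r; TRHT treated as a cut of pressure with prevalence p = 20–50%; share with ESS ≥ 9, q = 20–50%; two-sided 5% test.

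**1. The plan's own figure.** With a proportion of 0.5, n₀ = 1.96² × 0.25 / 0.10² = 96.04. The finite population correction gives 96.04 / (1 + 95.04/559) = 82.08, rounded up to 83. The figure reproduces, as a precision calculation for a proportion only.

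**2. If all 83 had both measurements.** Cutting a normal variable at prevalence p multiplies its correlation with ESS by a = φ(z)/√(p(1−p)), where z is the cut point. This gives a = 0.798 at p = 50%, 0.759 at 30% and 0.700 at 20%. Power is approximately Φ(√(n−3) × atanh(r) − 1.96), plus the negligible other tail.

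Worked case, r = 0.3: √80 × atanh(0.3) = 2.77, so power is Φ(0.81) = 79%. With p = 30%, r falls to 0.228, √80 × atanh(0.228) = 2.07, and power is Φ(0.11) = 55%.

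| r | Mean pressure on ESS score | TRHT yes/no on ESS score (p = 50 / 30 / 20%) | Loss, points |
|---|---|---|---|
| 0.1 | 15% | 11 / 10 / 10% | 4–5 |
| 0.2 | 44% | 30 / 28 / 24% | 14–20 |
| 0.3 | 79% | 59 / 55 / 48% | 20–31 |
| 0.4 | 97% | 84 / 80 / 73% | 13–24 |
| 0.5 | >99% | 97 / 95 / 91% | 3–9 |

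Simulation (8,000 runs per cell) agrees within a point or two: at r = 0.3, 80% against 49–60%, and losses of 12–30 points over r = 0.2–0.4. A second simulation, with prevalence 30–70% and integer ESS scores, gives 11–25 points. Together: about 11 to 30 points.

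**3. The design as written.** Only the ESS ≥ 9 subset has a 24h pressure: 83 × 0.20 ≈ 17 to 83 × 0.50 ≈ 42 participants. Their ESS range is also truncated. With λ = φ(z)/q, the ESS variance shrinks by v = 1 + zλ − λ², and the correlation becomes r√v / √(1 − r² + r²v). For q = 50%, v = 0.363, so r = 0.4 becomes 0.254; with 42 participants, √39 × atanh(0.254) = 1.62 and power is 37%. Simulation in the truncated subset, with TRHT prevalence 30–50%:

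| Share with ESS ≥ 9 (number) | r | Mean pressure | TRHT yes/no | Loss, points |
|---|---|---|---|---|
| 20% (17) | 0.3 | 9% | 5–7% | 2–4 |
| 20% (17) | 0.4 | 12% | 5–8% | 4–7 |
| 50% (42) | 0.3 | 22% | 14–17% | 5–8 |
| 50% (42) | 0.4 | 37% | 20–25% | 12–17 |

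The second simulation, at r = 0.3, gives a loss of 1–14 points. Together: about 1 to 17 points, with power at or below about 37% even when pressure is kept continuous.

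**The case against.** **The n = 83 loss is not the loss in this design.** This stands. Eighty-three pairs of ESS and 24h pressure do not exist while monitoring is limited to ESS ≥ 9. A reader might take the 11 to 30 points as the cost of the plan as it is; the documents do not support that.

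**ESS is not dichotomised in 12b.** This also stands. A reader might infer that the association will be tested as TRHT by ESS ≥ 9 and add a further loss for the second cut. Section 12b names the ESS score, no such two-by-two test is specified, and high risk of OSA is identified later, after ESS has been related to sleep fragmentation. Under the gate, ESS ≥ 9 would not vary among those monitored.

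**The question is about TRHT, a diagnosis.** The title, aim, hypotheses and primary outcome are all framed that way, so replacing TRHT with mmHg would change the question. This stands against substitution, but not against a companion analysis.

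**TRHT may not be a pure pressure cut.** The Background counts four drugs including a diuretic as resistant whatever the pressure, and defines hypertension by systolic or diastolic values. The calculations treat TRHT as one cut of one pressure, which favours the continuous analysis, and they use a single unadjusted correlation. The figures are therefore indicative.

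**Model form can be left to an SAP.** True of the link function, which 12b does not name. However, Sections 10 and 12b themselves fix TRHT status as the variable to which ESS is related.

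**Conclusion.** The point holds in a limited form. Section 12b relates ESS score to TRHT only as a status, although a mean pressure is available for everyone monitored and the rationale is graded.

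- With 83 complete pairs and a correlation of 0.2 to 0.4, the loss is about 11 to 30 points of power. At 0.1 or 0.5 it is under 10.
- With monitoring limited to ESS ≥ 9, the loss is about 1 to 17 points for correlations of 0.3 to 0.4, and power is low on either scale.

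These sizes rest on assumed correlations, prevalences and normality; the protocol supplies none of them. A reader might infer that continuous pressure would rescue the association analysis. It would not: the ESS ≥ 9 gate does more damage than the analysis scale and should be settled first. What remains is an inexpensive gain in information, worth most once the gate is resolved.

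**What to change.** Resolve first who receives 24h monitoring. Then, in Section 12b:

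- Keep TRHT status for the prevalence outcome.
- State that the association with OSA risk is estimated by logistic regression of TRHT on the ESS score, as the result that answers the stated aim.
- Prespecify beside it a linear regression of 24h mean systolic pressure on continuous ESS score, in all participants with a valid recording, adjusted for number of antihypertensive drugs. Report 24h mean diastolic pressure as supporting.
- State that a null TRHT result will not be read as no association without the pressure regression beside it.

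The cost is a wording change and one additional regression (with its diastolic counterpart) on data already downloaded, with no new measurement or participants. The small downside is that the added estimate is in mmHg per ESS point and concerns pressure on treatment, not the TRHT diagnosis, so the two results must be labelled accordingly.
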